13-30	Accrue sample and begin distribution of interventions and follow-up assessments
31-48	Continue distribution of GENERIC and eTARGET intervention and follow-up assessments;
49-54	Complete follow-up assessments through 18 months
55 – 60	Complete final data analysis and prepare reports

Protection of Human Subjects

1.RISKS TO HUMAN SUBJECTS

a. Human Subjects Involvement, Characteristics, Design

In Study I, approximately 92 participants will be recruited. In Phase I, we will recruit: (1) current dual users (of tobacco cigarettes and e-cigarettes) without interest in quitting smoking; (2) current dual users who have attempted, but not quit smoking; (3) current e-cigarette users who have successfully quit smoking; and (4) former dual users who have quit both products. Approximately 48 participants will be recruited across the 4 focus groups. In Phase II, up to 20 current dual users will be recruited for individual learner-verification interviews. In phase 3, 24 participants will be recruited across 2 focus groups. To be eligible for Study I, participants must: a) be \geq 18 years of age; b) be able to speak and read English; c) have \geq 1 year history of weekly smoking; and d) have \geq 1 month of e-cigarette use.

In Study II, we will recruit 2900 dual users and randomize them into the 3 treatment conditions. Inclusion criteria will be: (1) smoking at least one cigarette per week over the past year; (2) using e-cigarettes at least once per week over the past month; (3) age 18 or older; (4) not currently enrolled in a face-to-face smoking cessation program; and (5) able to speak and read English.

b. Sources of Research Material (to be used for research purposes only)

In Study I, research data will be derived from questionnaires measuring socio-demographic characteristics, smoking history, e-cigarette use history, nicotine dependence levels, and participant responses to the focus group and interview guides. In Study II, materials will include questionnaires measuring socio-demographic characteristics, smoking history, e-cigarette use history, nicotine dependence levels, motivation to quit measures, smoking expectancies, follow-up use of tobacco products, e-cigarettes, pharmacotherapies, other cessation aids and services, and breath carbon monoxide and saliva cotinine samples.

c. Potential Risks

Risks are judged to be extremely minimal. The intervention is a self-help approach and the focus groups and assessments are all self-report. Potential risks involve confidentiality and loss of privacy because participants may provide personal information about themselves during the focus groups and on screening or demographic questionnaires. Confidentiality will be maintained by using participant ID numbers on questionnaires, rather than names.

2.ADEQUECY OF PROTECTION AGAINST RISKS

a. Recruitment and Informed Consent

Participants will be weekly smokers recruited via multimedia advertisements (daily and weekly newspapers, radio, cable TV, social media, e-cigarette forums, etc.). Interested participants will be contacted and screened by a trained research assistant who will explain the purpose of the focus groups or interviews (in Study I) and explain the intervention study in detail and obtain verbal consent to participate (in Study II). Our research team has been successful with obtaining a waiver of written informed consent from the Institutional Review Boards (IRBs) of three institutions for our Forever Free RCTs. Research assistants will describe compensation, risks and benefits to participation, and confidentiality of the collected information, including that data will be shared with investigators and Moffitt Cancer Center. In Study II, the baseline questionnaire will include an introductory cover letter that contains a written explanation of the study and includes all the required elements of the informed consent. The letter will explain that returning the completed baseline questionnaire will be considered provision of informed consent. Informed consent and consenting procedures will adhere to the IRB guidelines.

b. Protections Against Risk

Potential risks involve confidentiality and loss of privacy because participants may provide personal information about themselves during the focus groups, as well as on assessment questionnaires. To minimize potential

risks all research assistants will receive training in research ethics. In addition, confidentiality will be maintained by using participant numbers on data, rather than participants' names. Participant data will be available only to research staff. Data will be kept in locked filing cabinets in locked laboratory rooms. Electronic data will be stored in password-protected database. Identifying information will not be reported.

3.POTENTIAL BENEFITS OF THE PROPOSED RESEARCH TO HUMAN SUBJECTS AND OTHERS

The potential risks are judged to be extremely minor. The main benefit of Study II is that participants may receive information to help them quit smoking and maintain abstinence. For participants in Study I or the assessment only condition of Study II, direct benefits of participation will be minimal. Participation may raise awareness regarding e-cigarette use, smoking, and cessation behaviors, and eventually lead to smoking cessation, with associated health benefits.

4.IMPORTANCE OF KNOWLEDGE TO BE GAINED

The proposed treatment development and clinical trial could potentially assist the large population of smokers who have already demonstrated initial action toward smoking cessation by commencing use of e-cigarettes. This naturally-occurring, self-selected, and motivated group may be primed to benefit from a minimal intervention that may enhance their chances of achieving and maintaining tobacco abstinence. The intervention was designed to be easy to disseminate and implement, and cost-effectiveness data should aid stakeholders in making implementation decisions.

5.DATA SAFETY AND MONITORING PLAN

This is an extremely minimal risk study. Nevertheless, the principal investigator, [name], will implement a DSMP to ensure that the expected risk/benefit ratio is maintained throughout the study and that the confidentiality and accuracy of the data are preserved. All members of the study team will receive formal training in research ethics and HIPAA procedures through the University of South Florida IRB, as well as study-specific training provided during research team meetings. The study team will meet weekly to discuss study progress, including participant recruitment and retention, data management, any participant complaints, and confidentiality issues. In addition, study progress will be tracked by Moffitt Cancer Center's Protocol Review and Monitoring Committee (PRMC). The probability of an adverse event occurring in this study is extremely low, given the nature of the study. However, as per IRB policy, any serious or unexpected adverse events will be reported promptly (within 2-5 business days, depending on the nature of the event) to the IRB and the PRMC. A summary of the adverse events that occurred during the previous year will be included in the annual progress report to NIH.

Inclusion of Women and Minorities

Inclusion of Women

Our self-help intervention studies typically attract a sample comprising approximately 60% women, representing women's greater willingness to seek assistance. We expect a similar gender distribution in the proposed study.

Inclusion of Minorities

Study I

The Tampa Bay area is racially/ethnically diverse. Based on similar studies we have conducted with a community sample, and recent data indicating that e-cigarette use rapidly becoming more evenly across racial and ethnic groups (King et al., 2013), we anticipate that 71% of the sample will be Caucasian, 20% will be African American, 1% American Indian/Alaska Native, 1% Pacific Islander, 1% Asian, and 6% other (more than one/unreported). We expect that 11% of the local sample will be Hispanic.

Study II

Based on our previous studies with "Forever Free" self-help interventions with national recruitment, including our cessation study currently in progress (C.1.2.3), as well as data on the racial and ethnic distribution of e-cigarette use (King et al., 2013), we estimate that 64% will be Caucasian, 30% will be African American, 1% American Indian/Alaska Native, 1% Pacific Islander, 1% Asian, and 3% other (more than one/unreported). We expect that 6% of the national sample will be Hispanic.

The "Targeted/Planned Enrollment Table" displays the expected racial and ethnic distributions for each study.

Planned Enrollment Report

Study Title:

Smoking Cessation Self-Help for Dual Users of Tobacco Cigarettes and E-Cigarettes (Study I)

Domestic/Foreign:

Domestic

Comments:

De siel Oste veries					
Racial Categories	Not Hisp	oanic or Latino	Hispan	Tota	
	Femal	Mal	Femal	Mal	I
American Indian/Alaska Native	0	1	0	0	1
Asia	1	0	0	0	1
Native Hawaiian or Other Pacific	1	0	0	0	1
Black or African American	10	6	1	1	18
Whit	36	24	4	2	66
More than One Race	2	1	1	1	5
Tota	50	32	6	4	92

Study 1 of 2

Planned Enrollment Report

Study Title:

Smoking Cessation Self-Help for Dual Users of Tobacco Cigarettes and E-Cigarettes (Study II)

Domestic/Foreign:

Domestic

Comments:

De siel Oste namie s					
Racial Categories	Not Hisp	anic or Latino	Hispan	Tota	
	Femal	Mal	Femal	Mal	
American Indian/Alaska Native	15	10	0	0	25
Asia	15	10	0	0	25
Native Hawaiian or Other Pacific	15	10	0	0	25
Black or African American	44	294	9	6	750
Whit	88	592	72	48	160
More than One Race	36	24	9	6	75
Tota	141	940	9	60	250

Study 2 of 2

Inclusion of Children

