Specific Aim 1. To create a minimal smoking-cessation intervention for current dual users of tobacco cigarettes and e-cigarettes (Study I). The intervention will comprise a series of booklets modeled after the *Forever Free* booklets found to be successful at producing long-term abstinence among the general population of smokers, but adapted to the special needs, circumstances, and risk factors of dual users. Validated methodologies used for adapting the intervention mirror those used in our prior smoking cessation studies, and reflect systematic approaches across three-phases informed by focus group and learner verification methodologies. The intervention will provide assistance for smoking cessation, and also encourage users to taper and eventually terminate their e-cigarette use as per traditional NRT. The end product of Study I will be a series of booklets tentatively titled, *"If You Vape: Guide to Quitting Smoking,"* available both in printed and electronic formats.

Specific Aim 2. To evaluate the efficacy of the intervention via a randomized, controlled clinical trial of current dual users (Study II). We will compare the intervention developed under Specific Aim 1 with both an assessment-only condition and a generic self-help condition comprising existing smoking cessation booklets. We hypothesize that recipients of our targeted *If You Vape* booklets will show higher rates of tobacco abstinence at 6, 12, 18, and 24 months after enrollment, as compared to both comparison conditions. A secondary hypothesis is that the new intervention will produce higher rates of abstinence from e-cigarettes themselves. To identify mechanism of change, we will also test several *a priori* moderator and mediator variables, including gender, socio-economic status, motivation to quit, nicotine dependence, e-cigarette expectancies, and magnitude of e-cigarette use (frequency, dosage).

Specific Aim 3. To calculate and compare the cost-effectiveness of the interventions. Costeffectiveness data are vital for evaluating the real-world feasibility of an intervention. Small improvements in treatment efficacy may not be justified if they require substantially greater cost. We will compare the interventions not only on outcome efficacy, but on cost-effectiveness with respect to cost per incremental cessation and expected life-years saved.

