 - d) Item 9: response of 'I do not smoke'; e) Item 10: response of 'I do not smoke';
 - f) Item 11: response of 'I do not smoke'; g) Item 15: response of 'I do not smoke';
 - h) Item 16: response of 'I do not smoke'; h) Item 22: response of 'I do not smoke'.

Those with the following responses will be excluded based on **Criterion #2** (e-cigarettes use \geq 1/week over the past month).

Rule 3) Marked the designated answer to any two or more of the following in the 'E-Cigarette' section: a) Item 1: response of 'Less than 1 month ago'; b) Item 2: response of 'No use in the past month'; c) Item 3: response of 'Not applicable - no use in past month'

Those with the following response will be excluded based on **Criterion #3** (age \geq 18 years).

Rule 4) Computed difference between date of survey completion and date of birth is less than 18 years.

Those with the following response will be excluded based on **Criterion #4** (not currently enrolled in a face-to-face smoking cessation program).

Rule 5) Marked 'Currently use' to the item assessing in-person counseling or support program.

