At each assessment point we will calculate point-prevalence abstinence rates (for tobacco smoking as well as e-cigarette use) using 7-day, 30-day, and 90-day criteria. Point-prevalence measures are best for capturing the dynamic nature of cessation, maintenance, and relapse. The 7-day criterion will serve as our primary outcome index. Continuous abstinence is not feasible because guit dates will be highly variable across participants, and also because one goal of the intervention is to encourage lapsers to guit again (recycle). We need our outcome measures to reflect these changes in smoking status over time. However, the 30-day and 90-day point-prevalence abstinence criteria also reflect more prolonged abstinence than the 7day criterion usually used in treatment studies (Velicer et al., 1992). We will also compare groups on continuous measures, such as current smoking rate (cigarettes/day), months of smoking during the follow-up period, length of current abstinence period, and latency from quit date to relapse. Outcomes will be reported that account for missing follow-up data using both multiple imputation (MI) and intent-to-treat (ITT) approaches.

C.5. Cost-Effectiveness Analysis (Aim 3)

The relative effectiveness and costs of the intervention compared to standard care will be measured based on the health care system perspective. Using the trial endpoint results, effectiveness will be predicted in terms of smoking cessation and translated into life years and quality adjusted life years (QALY) based on published associations between smoking cessation and long-term health outcomes (Cohen & Fowler, 1993; Torrance, 1986). Costs include the intervention costs, collected prospectively, and lifetime costs of reduced medical expenditures attributable to smoking cessation, that will be modeled using published estimates (e.g., Berman et al., 2013; Cowan & Schwab, 2011; Fishman et al., 2003; Hockenberry et al., 2012; Hodgson, 1992; Oster et al., 1984). No out-of-pocket costs or transfer payments (i.e., increased social security due to longevity) will be incorporated into the analysis, because they do not fall within the system perspective. In addition, costs associated only with research (e.g., mailing of assessments) will be excluded. Monetary values will be inflation adjusted, and all outcomes will be presented in discounted and undiscounted values.

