C.6.4.2. Specific Aim 2. Generalized estimating equations (GEE) will be used to fit populationaveraged models to handle the longitudinally measured binary outcomes, with the main covariates of intervention conditions, time (months from baseline), and the interaction of condition and time. Potential confounding variables (e.g., group differences in demographic, smoking history, or pharmacotherapy use) that appear despite randomization will be adjusted for in the model. Pair-wise condition and time interval comparisons will be tested using the generalized score statistics from GEE models by utilizing the contrast statements. Further, the generalized linear mixed effects models with a logit link function will be expanded, including the participant-specific intercept and slopes as the random effects in the model. Moderators (e.g., gender, SES, quitting motivation, nicotine dependence, magnitude of e-cigarette use, expectancies)will be tested via interactions with condition and condition x time. *Mechanisms of change associated with treatment*

will be tested (e.g., motivational measures, intervention usage, e-cigarette usage) via mediation analysis, performed using Hayes' (2009) "Indirect" macro within SAS. The approach described above will be used to evaluate the primary outcome of smoking cessation as well as the secondary outcome of e-cigarette cessation.

We will extend our analysis to lapse/recovery models using the Kaplan-Meier method with log-rank test for the stratified sub-groups (e.g., lapsed and recovered groups) to test the effect of intervention condition and Cox PH models controlling potential confounding variables.

To capture proportional shifts in cigarette vs. e-cigarette use, we will create a response variable with multiple levels for each follow-up assessment reflecting the relative level of e-cigarette to cigarette use, referenced against baseline use of each product. The multi-level outcome variable will be fitted using a logistic analysis on the generalized logits to test if the interventions have a significant impact on these shifts.

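### For e-cigarette cessation, the 7-day index is no longer than the once-a-week vaping entry floor, so near-weekly vapers who only taper can be scored as having quit

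*Combined protocol and SAP*

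**What the plan says.** **Outcome.** C.4.2 commits to calculating "point-prevalence abstinence rates (for tobacco smoking as well as e-cigarette use) using 7-day, 30-day, and 90-day criteria" at every assessment, and then says: "The 7-day criterion will serve as our primary outcome index". It names no separate index for vaping. C.6.4.2, after setting out the GEE and mixed-model analysis, adds: "The approach described above will be used to evaluate the primary outcome of smoking cessation as well as the secondary outcome of e-cigarette cessation". The hypothesis at stake is in Specific Aim 2: "A secondary hypothesis is that the new intervention will produce higher rates of abstinence from e-cigarettes themselves".

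**Entry.** The Study II inclusion criteria (C.3.2, and again in Protection of Human Subjects, 1.a) accept anyone "using e-cigarettes at least once per week over the past month".

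**Baseline re-check (C.4.1.2).** For smoking, Rule 1 removes anyone reporting cigarettes on only one to five days a month. For vaping, Rule 3 needs two of three answers: a start less than a month ago, or "b) Item 2: response of 'No use in the past month'; c) Item 3: response of 'Not applicable - no use in past month". None of these removes someone who vapes on only a few days a month.

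**Intervention.** Under Specific Aim 1 the booklets will "encourage users to taper and eventually terminate their e-cigarette use as per traditional NRT", and C.2.6 has the advice to stop vaping grow stronger through the series.

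**The concern.** For vaping, the lightest eligible pattern (one use in a week) and the definition of success (none in a week) are neighbouring values over windows of equal length. Neither a minimum change nor confirmation at a second survey is required. Two errors can follow.

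- **Tapering scored as cessation.** A vaper who falls below weekly use but has not stopped will often have an empty 7-day window. Because the targeted booklets promote tapering, this can differ by arm and appear as a cessation effect for eTARGET. Were vaping among continuing light users to rise in eTARGET instead, for example after giving up cigarettes, the distortion would run the other way.
- **Chance gaps in unchanged use.** An irregular weekly vaper may happen not to vape in the 7 days before a survey. This adds false quitters to every arm and blurs the contrast.

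The primary smoking outcome is largely protected by Rule 1. The point concerns the secondary hypothesis on e-cigarettes.

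**Working it through.** The plan states no rate, sample size or power for e-cigarette cessation, so there is no planned figure to reproduce.

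**Inputs from the documents.** Entry floor of once a week; windows of 7, 30 and 90 days; 826 per arm for GENERIC and eTARGET (C.6.2).

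**Assumptions.** The spacing of use, the share of near-weekly vapers and the true quit rates are not given, so ranges are shown.

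**Step 1. Chance of an empty window of w days at r uses per week.** Three models: Poisson, exp(−rw/7); independent days, (1 − r/7)^w; evenly spaced use, max(0, 1 − rw/7).

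| Pattern at survey | 7 days | 30 days | 90 days |
|---|---|---|---|
| Twice a week | 0–14% | about 0 | about 0 |
| Once a week | 0–37% (34% independent days) | 0–1.4% | about 0 |
| Once a fortnight | 50–61% | 0–12% | 0–0.2% |
| Once in 4 weeks | 75–78% | 0–34% | 0–4% |

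**Step 2. Unchanged vapers who vape every week.** Under independent days, the chance of some use in each of four successive weeks is (1 − 0.340)^4 = 0.19. About 81% of such people would therefore miss the entry criterion, if it is read as use in every week. With exactly one randomly placed day per calendar week, the chance of an empty 7-day window, averaged over survey day o = 0 to 6, is the mean of o(7 − o)/49 = 56/343 = 16%. With use in every 7-day span it is 0%. The range for these vapers is therefore 0% to 16%.

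**Step 3. False quits per arm from unchanged vapers.** Share × chance. A 5% share gives 0 to 1.8 points (0.05 × 0.368). A 30% share gives 0 to 11.0 points (0.30 × 0.368), or at most 4.9 points if they vape every week (0.30 × 0.163).

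**Step 4. Dilution.** Assume true quitting of 15% vs 20%, 826 per arm, one visit, two-sided .05 and a 20% share of weekly vapers. Observed rate = t + (1 − t) × 0.20 × f, where f is the chance of an empty window.

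- 7 days, f = 0.340: 20.8% vs 25.4%, power 61%.
- 7 days, f = 0.163: 17.8% vs 22.6%, power 69%.
- 30 days, f = 0.0098: 15.2% vs 20.2%, power 76%; about 70% if 10% of true quitters stopped too recently to count.

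**Step 5. Differential tapering with no extra quitting (826 per arm, .05).**

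- *Weekly to fortnightly.* True quitting 10% in both arms, 20% weekly vapers, all of whom halve their use in eTARGET only, Poisson. On 7 days: 0.10 + 0.90 × 0.20 × 0.368 = 16.6% vs 0.10 + 0.90 × 0.20 × 0.607 = 20.9%, significant about 61% of the time. On 30 days: 10.2% vs 12.1%, about 22%. With a 10% share the 7-day rates are 13.3% vs 15.5%, about 24%.
- *Twice to once a week.* 20% vape twice weekly and half of them drop to once in eTARGET only, independent days. With no true quitting: 0.20 × 0.095 = 1.9% vs 0.20 × (0.5 × 0.095 + 0.5 × 0.340) = 4.3%, significant about 82% of the time. With 5%, 10% or 15% true quitting in both arms this falls to 42%, 27% or 20%.

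**The case against.** The strongest reply has four parts.

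**Unchanged vapers.** A reader might infer that eligible weekly vapers who change nothing will be counted as quitters, a third of them at each survey. The documents do not support that. The 34% comes from a model under which most such people would not have vaped in each week of the entry month, and the figure is 0% to 16% for those who do. The error is also expected to be equal across randomised arms, so by itself it creates no difference. This part stands. It does not answer the tapering problem: evenly spaced weekly users are never miscounted while unchanged, but after tapering to fortnightly half of them are.

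**Power.** With the 16% figure, 7-day power is 69%, against 70% to 76% on 30 days. Dilution alone is a weak reason to change the window. This also stands.

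**Existing safeguards.** The 30- and 90-day criteria are calculated, magnitude of e-cigarette use is a planned moderator, and C.6.4.2 has a multi-level variable for shifts between products. These would help to expose an artefact, but they do not change which window is the index.

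**Scope of the index.** C.4.2 speaks of a primary outcome index and justifies it by smoking status, so it may have been meant for cigarettes only. On that reading e-cigarette cessation has three candidate windows and none named, while C.6.3 applies no multiplicity adjustment to secondary analyses. Either reading needs a sentence in the plan.

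**Conclusion.** The point holds for the secondary outcome. The entry floor and the index window are both one week, light vapers are not removed, and the intervention promotes the behaviour that the index can misread. Per tapering vaper the effect is large: 50% to 61% scored abstinent at once a fortnight on 7 days, against 0% to 12% on 30 days.

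The effect on the trial result cannot be fixed from the documents. It depends on the share of near-weekly vapers and on how much tapering differs between arms. The 34% miscount, the 61% power and the 61% and 82% taper results are upper-range illustrations; the 82% needs zero true quitting and is about 27% with 10% quitting in both arms. All power figures are single-visit approximations and ignore the repeated-measures model.

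A reader might go further and infer that chance gaps favour eTARGET, or that any positive e-cigarette result would be an artefact. Neither follows: chance gaps only dilute, and bias requires differential tapering, whose size is unknown.

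**What to change.** In C.4.2 and C.6.4.2:

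1. Keep 7-day point prevalence as the index for cigarette smoking.
2. Name the 30-day criterion, already calculated at each assessment, as the index for e-cigarette cessation. It also matches the one-month reference period of the vaping entry criterion.
3. Report 7-day e-cigarette abstinence as supportive, by baseline vaping frequency (weekly, several days a week, daily).
4. Prespecify baseline vaping frequency as a covariate in the e-cigarette model.

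The cost is wording only, since current e-cigarette use is already assessed at baseline. The downsides are longer recall and the loss of people who stopped 7 to 29 days before a survey. If near-weekly vapers are rare and 10% of quitters are too recent, power in the 15% vs 20% example falls from 76% to 71% (13.5% vs 18.0%). The 30-day window reduces the tapering problem without removing it: at one use in four weeks, up to 34% would still be scored abstinent. The 90-day result is therefore worth showing alongside.
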